**ATP Level and Cough Sensitivity to ATP in Subjects with Refractory/Unexplained Chronic Cough**

**NCT05265871**

**April 25, 2025**

**Study Protocol**

## **Subjects and Study Design**

Patients with RCC/UCC were recruited in the Cough Clinic at the First Affiliated Hospital of Guangzhou Medical University from May 2022 to January 2024. According to Chinese guideline, RCC/UCC referred to a chronic cough: 1) without identifiable causes after throughout investigation; 2) persistent after empirical treatment to known causes; 3) persistent after treatment for positive conditions known to be associated with chronic cough. The diagnosis of RCC/UCC strictly adhered to the criteria above. Other inclusion criteria included: 1)  $\geq 18$  years old; 2) cough as sole symptom lasting  $\geq 6$  months; 3) cough visual analogue score  $\geq 30$ mm. Age and gender matched healthy controls ( $\geq 18$  years old) would be recruited.

For all subjects, exclusion criteria were as follow: 1) smoking currently or in the past 6 months, or a smoking history of  $>20$  pack-year; 2) a forced expiratory volume in 1 second/forced vital capacity ratio  $<70\%$ ; 3) positive findings of chest radiography; 4) use of inhaled/oral corticosteroid, bronchodilators, anti-allergic medicine, antitussive medicine or anti-reflux treatment in the past 1 week; 5) a history of acute respiratory infection in the past 4 weeks; 6) a history of severe disease (cancer, acute coronary syndrome and so on). Additionally, any signs of cough hypersensitivity would lead to exclusion of healthy controls.

Clinical features recording, chest radiography, routine blood test, pulmonary function tests, induced sputum test, ATP cough challenge and capsaicin cough challenge were performed to all subjects. Supernatant of sputum were stored at  $-80^{\circ}\text{C}$  for the further ATP measurement. Capsaicin cough challenge was performed at least 30min after ATP cough challenge. All subjects were informed of the study procedures and provided written informed consent. The study was approved by the Ethics Committee of the First Affiliated Hospital of Guangzhou Medical University (No. ES-2023-027-01).

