### **Cough challenge**

ATP cough challenge was performed firstly and capsaicin cough challenge was following with an interval of at least 30min. ATP solutions (Sigma-Aldrich, USA) were prepared with 0.9% saline as solvent, with concentrations ranged from 0.1 mM, 0.316 mM, 1 mM, 3.16 mM, 10 mM, 31.6 mM, 100 mM and 316 mM. The solutions were stored in refrigerator at 4°C and were re-prepared every three days. Capsaicin cough challenge was performed with capsaicin (Sigma Aldrich, Seattle, USA) solutions beginning at a concentration of 1.95  $\mu$ M and then doubling the concentration up to 1000  $\mu$ M as described previously. Concentration–response challenges to inhaled ATP and capsaicin were undertaken with a compressed air driven nebulizer. Briefly, the single-breath dose-response method was adopted using a compressed air-driven nebulizer controlled by a breath-activated dosimeter (APS, JAEGER) whose output and duration of each nebulization were 160 mg/min (calculated as 0.9% saline) and 0.5 seconds, respectively. Coughs in the first 30 seconds after each inhalation recorded. The termination of cough challenge was the inhalation of the solution of highest concentration. The lowest concentration that provoked at least 2 coughs (C2) and the lowest concentration that provoked at least 5 coughs (C5) were recorded. For capsaicin, C5 of the healthy subjects was  $\geq$ 125  $\mu$ M, so hypersensitivity to capsaicin was defined as C5<125  $\mu$ M.

1. [Chinese expert consensus on the diagnosis and treatment of chronic refractory cough]. Zhonghua Jie He He Hu Xi Za Zhi. 2021;44(8):689-98. doi: 10.3760/cma.j.cn112147-20210320-00186. PubMed PMID: 34645134.
2. Zhan W, Luo W, Zhang Y, Xiang K, Chen X, Shen S, Huang C, Xu T, Ding W, Chen Y, Lin M, Pan

X, Lai K. Sputum Transcriptomics Reveals FCN1+ Macrophage Activation in Mild Eosinophilic Asthma Compared to Non-Asthmatic Eosinophilic Bronchitis. *Allergy Asthma Immunol Res.* 2024;16(1):55-70. doi: 10.4168/aaair.2024.16.1.55. PubMed PMID: 38262391; PMCID: PMC10823142.

3. [Chinese national guideline on diagnosis and management of cough(2021)]. *Zhonghua Jie He He Hu Xi Za Zhi.* 2022;45(1):13-46. doi: 10.3760/cma.j.cn112147-20211101-00759. PubMed PMID: 35000304.

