ATP Level and Cough Sensitivity to ATP in Subjects with Refractory/Unexplained Chronic Cough

NCT05265871

April 25, 2025

Statistical Analysis Plan

IBM SPSS Statistics version 26 was used for analysis. Concentrations of ATP and capsaicin were log-transformed (Lg) for calculation. Normal distribution data was presented as mean±standard deviation, while median (interquartile range) for skewed data. Data were compared by independent-samples t test, Mann-whitney U test or chi-square test. Correlation analysis was conducted using Pearson correlation coefficient. A P value < 0.05 was considered statistically significant.

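### Controls are matched on age and gender but the group comparisons are unadjusted; adding both factors is a cheap improvement, not the repair of an error

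*Protocol*

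**What the plan says.** The protocol, under Subjects and Study Design, says that "Age and gender matched healthy controls" would be recruited. It does not say whether matching is individual or at group level, and gives no ratio or age tolerance.

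The SAP is one paragraph. On group comparisons it says: "Data were compared by independent-samples t test, Mann-whitney U test or chi-square test". Its only other method is a bivariate one: "Correlation analysis was conducted using Pearson correlation coefficient". The threshold is "A P value < 0.05 was considered statistically significant", with sidedness not stated. No covariate, stratum, pair or regression model appears. No test is assigned to a named endpoint, so sputum ATP, C2 and C5 can only fall under the one general sentence.

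The Cough challenge section fixes the ATP concentrations as eight half-log steps ending in "31.6 mM, 100 mM and 316 mM", and adds: "The termination of cough challenge was the inhalation of the solution of highest concentration". C2 and C5 are therefore ordered steps with a ceiling.

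**The concern.** By matching, the sponsor treated age and gender as worth controlling. The study is not randomised, and matching is the only control for these two factors that the documents describe. The analysis then makes no use of them. Two things could follow:

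- **Close matching, factors predict the outcome.** The design has removed age and gender variation from the group difference, but the standard error still counts it. P values are too large and power is lost.
- **Loose matching, factors predict the outcome.** Part of the group difference reflects age and gender, and nothing in the analysis removes it.

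If the factors do not predict the outcome, almost nothing is gained or lost either way. The documents do not show which case applies.

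**Working it through.** **Inputs.** From the documents: the matching factors, the tests, the 5% level, the log scale and the eight ATP steps from 0.1 to 316 mM. Assumed: two-sided tests; 50 per group (20 and 100 as a range); outcome SD 1; true difference 0.5 SD for power; R² from 0 to 0.3, split equally between age and gender; gender SD 0.5. The plan has no figure to reproduce.

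**1. Close matching.** The group difference has true standard error √((1−R²)·2/n). The unadjusted t test rejects beyond t(98)·√(2/n) = 1.984 × 0.200 = 0.397.

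- R² = 0.1: SE = √(0.9 × 0.04) = 0.190. Type I error: 0.397/0.190 = 2.09, two-sided 3.7%. Unadjusted power: (0.5 − 0.397)/0.190 = 0.54, or 71%. Adjusted power: 0.5/0.190 − 1.985 = 0.65, or 74%.
- R² = 0.3: SE = √(0.7 × 0.04) = 0.167. Type I error: 0.397/0.167 = 2.37, two-sided 1.8%. Unadjusted power: 0.62, or 73%. Adjusted power: 1.00, or 84%.

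Simulation (10,000 replicates) gives type I error of 3.8% and 2.1%, and power of 71% versus 74% and 74% versus 85%. At R² = 0 power is 70% either way. Across R² from 0 to 0.3 the gain from adjusting is 0 to 14 points at 20 per group and at most 2 at 100.

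**2. Loose matching, realised gaps held fixed.** Bias = √(R²/2) × (age gap in SD + gender gap/0.5). Unadjusted type I error = P(Z > (0.397 − bias)/SE) + P(Z > (0.397 + bias)/SE).

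| Gaps | Bias, R² = 0.1 | Type I error | Bias, R² = 0.3 | Type I error |
|---|---|---|---|---|
| 0.3 SD and 10 points, aligned (0.3 + 0.2 = 0.5) | 0.112 | 7.0% | 0.194 | 11.2% |
| 0.3 SD and 10 points, opposing (0.3 − 0.2 = 0.1) | 0.022 | 3.8% | 0.039 | 2.1% |
| 0.1 SD and 5 points, aligned (0.1 + 0.1 = 0.2) | 0.045 | 4.2% | 0.077 | 3.0% |

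For the first row at R² = 0.1, the two limits are 1.50 and 2.68, so 6.6% + 0.4% = 7.0%. At R² = 0, 0.05 and 0.2 that row gives 4.7%, 5.9% and 9.2%.

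**3. The same gaps as expectations only.** If realised gaps vary as in unmatched samples, the aligned 0.3 SD/10-point case gives 8.2% and 15.6%. Opposing gaps give 4.7–6.3% over 20, 50 and 100 per group, and the small aligned gaps at most 6.5% at 50 per group. Adjusted type I error is 4.6–5.4% throughout, but the data were generated from the fitted model.

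**4. ATP C5.** Latent log10 C5 (SD 0.8) was cut at the protocol's eight steps, plus a not-reached category, at 50 per group.

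- Close matching, Mann-Whitney versus proportional-odds power: 66% versus 71% (R² = 0.1) and 69% versus 82% (R² = 0.3) if 20% of controls do not reach C5; 63% versus 67% and 63% versus 77% if 50% do not.
- Aligned 0.3 SD/10-point gaps held fixed, Mann-Whitney type I error: 6.3–7.0% (R² = 0.1) and 10.5–10.6% (R² = 0.3).
- Proportional-odds type I error, with gaps free to vary: 4.3–6.1% at 50 per group and 4.8–6.8% at 20.

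**5. Cost if R² = 0 and gaps are 0.3 SD/10 points.** Linear-model power falls from 34% to 32% (20 per group), 69% to 67% (50) and 94% to 93% (100). Proportional-odds loses about 1 point at 50.

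**The case against.** The strongest reply is that the plan contains no error. Tests for independent samples suit group-level matching. Close matching protects the comparison by design, and the unadjusted test then errs on the cautious side. Material inflation needs three things together: strong predictors, gaps left after matching, and gaps that push the same way. The documents support none of them. All of this stands.

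A reader might infer more, in four ways:

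- **That the matching factors play no part.** They act through the selection of controls.
- **That a paired analysis is required.** The documents do not say that individual pairs were formed.
- **That false positives run at 8% to 16%.** Those figures let gaps vary as if there were no matching, which is not the stated design. With the same gaps held fixed they are 7% and 11%, and those still rest on assumed predictors and gaps.
- **That adjustment makes cases and controls comparable.** The protocol also states that "any signs of cough hypersensitivity would lead to exclusion of healthy controls". That selection can itself create C2 or C5 differences. It is a separate issue, adds no weight here, and is not addressed by adjusting for age and gender.

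The reply does not remove the point that matching quality is undocumented, and that a model using both factors costs little whichever case applies.

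**Conclusion.** The point holds as a recommended improvement. The plan matches on two factors and leaves them out of every comparison; this is less efficient if matching was close and leaves residual confounding if it was loose. Under the assumptions above, at 50 per group, adjusting gains about 3 points of power at R² = 0.1 and about 10 at R² = 0.3 for sputum ATP with close matching. It also removes a type I error of about 7% to 11% in the unfavourable loose case. With opposing or small gaps there is little or no inflation to remove. None of these sizes can be taken from the documents, so they do not show that any comparison in this study is biased. Confidence is moderate.

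**What to change.** - Compare log sputum ATP by linear regression on group, age (continuous) and gender.
- Compare C2 and C5 by proportional-odds or interval-censored regression with the same terms. Subjects who do not reach the endpoint at the top concentration go in the highest category or are right-censored.
- Report adjusted differences or odds ratios with 95% CIs beside the planned unadjusted tests.
- State the matching type, ratio and age tolerance, and report age and gender by group. Use a matched-set analysis only if individual pairs were formed and recorded.
- State that the adjustment does not deal with the exclusion of hypersensitive controls.

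**Cost.** No new data should be needed, since matching requires age and gender to be known. About 1 to 3 points of power are lost if the factors are unrelated to outcome and matching was loose. The proportional-odds test may be slightly liberal at about 20 per group.

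**Timing.** Patients were recruited "from May 2022 to January 2024" and both documents are dated April 25, 2025. If results have been seen, label the adjusted analysis as added at this version and report it as a sensitivity analysis, not as a replacement for the planned tests.

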## **ATP measurement in Induced sputum**

Sputum was induced and processed as described previously. Briefly, sputum was induced with 3% saline. Sputum plugs were selected and mixed with four times its volume of 0.1% dithiothreitol. The cell smear was stained with hematoxylin-eosin. The differential cell count was obtained by

counting 400 non-squamous cells. Supernatant was stored in -80°C for the following measurement of ATP. The ATP level was measured using the ATPlite 1-Step Luminescence Assay System (Revvity, USA), following the provided instructions. The briefly procedure for using a 96-well microplate to measure ATP involves equilibrating the substrate and buffer at room temperature, reconstituting the lyophilized substrate solution with buffer, adding 100  $\mu$ L of the reconstituted reagent to each well containing 100 $\mu$ L induced sputum supernatant, shaking the microplate for 2 minutes, and then measuring luminescence.

### **Cough challenge**

ATP cough challenge was performed firstly and capsaicin cough challenge was following with an interval of at least 30min. ATP solutions (Sigma-Aldrich, USA) were prepared with 0.9% saline as solvent, with concentrations ranged from 0.1 mM, 0.316 mM, 1 mM, 3.16 mM, 10 mM, 31.6 mM, 100 mM and 316 mM. The solutions were stored in refrigerator at 4°C and were re-prepared every three days. Capsaicin cough challenge was performed with capsaicin (Sigma Aldrich, Seattle, USA) solutions beginning at a concentration of 1.95  $\mu$ M and then doubling the concentration up to 1000  $\mu$ M as described previously. Concentration–response challenges to inhaled ATP and capsaicin were undertaken with a compressed air driven nebulizer. Briefly, the single-breath dose-response method was adopted using a compressed air-driven nebulizer controlled by a breath-activated dosimeter (APS, JAEGER) whose output and duration of each nebulization were 160 mg/min (calculated as 0.9% saline) and 0.5 seconds, respectively. Coughs in the first 30 seconds after each inhalation recorded. The termination of cough challenge was the inhalation of the solution of highest concentration. The lowest concentration that provoked at least 2 coughs (C2) and the lowest concentration that provoked at least 5 coughs (C5) were recorded. For capsaicin, C5 of the healthy subjects was  $\geq$ 125  $\mu$ M, so hypersensitivity to capsaicin was defined as C5<125  $\mu$ M.

1. [Chinese expert consensus on the diagnosis and treatment of chronic refractory cough]. Zhonghua Jie He He Hu Xi Za Zhi. 2021;44(8):689-98. doi: 10.3760/cma.j.cn112147-20210320-00186. PubMed PMID: 34645134.
2. Zhan W, Luo W, Zhang Y, Xiang K, Chen X, Shen S, Huang C, Xu T, Ding W, Chen Y, Lin M, Pan

X, Lai K. Sputum Transcriptomics Reveals FCN1+ Macrophage Activation in Mild Eosinophilic Asthma Compared to Non-Asthmatic Eosinophilic Bronchitis. *Allergy Asthma Immunol Res.* 2024;16(1):55-70. doi: 10.4168/aaair.2024.16.1.55. PubMed PMID: 38262391; PMCID: PMC10823142.

3. [Chinese national guideline on diagnosis and management of cough(2021)]. *Zhonghua Jie He He Hu Xi Za Zhi.* 2022;45(1):13-46. doi: 10.3760/cma.j.cn112147-20211101-00759. PubMed PMID: 35000304.

ATP Level and Cough Sensitivity to ATP in Subjects with Refractory/Unexplained Chronic Cough

NCT05265871

April 25, 2025

Statistical Analysis Plan

IBM SPSS Statistics version 26 was used for analysis. Concentrations of ATP and capsaicin were log-transformed (Lg) for calculation. Normal distribution data was presented as mean±standard deviation, while median (interquartile range) for skewed data. Data were compared by independent-samples t test, Mann-whitney U test or chi-square test. Correlation analysis was conducted using Pearson correlation coefficient. A P value < 0.05 was considered statistically significant.

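### Does one 0.05 rule for every test, with no primary endpoint and ATP C2 and C5 unranked, require a multiplicity correction?

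*SAP*

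**What the plan says.** The SAP is a single paragraph. For group differences it says "Data were compared by independent-samples t test, Mann-whitney U test or chi-square test"; for associations, "Correlation analysis was conducted using Pearson correlation coefficient"; and for inference, "A P value < 0.05 was considered statistically significant". No endpoint is attached to any test. The number of correlations and the pairs of variables are not listed.

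Three measurements bear directly on the study title. In the Protocol, the section on ATP measurement in induced sputum states "The ATP level was measured using the ATPlite 1-Step Luminescence Assay System". The section on the cough challenge states "The lowest concentration that provoked at least 2 coughs (C2) and the lowest concentration that provoked at least 5 coughs (C5) were recorded". C5 is singled out once, for the other challenge agent: "hypersensitivity to capsaicin was defined as C5" below a fixed cut-off. There is no equivalent rule for ATP, so that sentence does not rank ATP C5 above ATP C2.

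The title itself names two targets: the level of ATP, and cough sensitivity to ATP. Patients were recruited "from May 2022 to January 2024", and both documents are dated April 25, 2025.

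**The concern.** A 0.05 rule applied test by test limits the error of each test to 5%. It does not limit the chance that at least one of several tests is called significant when nothing differs. With no primary endpoint, a difference in ATP C2, in ATP C5 or in sputum ATP could each be reported as a significant finding.

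The two thresholds raise a more specific difficulty. If only one of C2 and C5 falls below 0.05, the documents do not say whether cough sensitivity to ATP differed, and that is one of the two questions in the title. A reader also could not tell whether the emphasised threshold was chosen before or after the results were seen. The SAP is written in the past tense and dated after recruitment closed, which adds to that doubt.

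**Working it through.** **Inputs.** The per-test level of 0.05 is from the SAP. Sidedness is not stated, so two-sided is assumed. The documents give no sample size, no power and no correlations between measures. They therefore contain no derived figure to reproduce, and every correlation below is an assumption.

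**1. Limits under independence.** The chance of at least one P<0.05 among k independent true nulls is 1 - 0.95^k:
- two tests: 1 - 0.9025 = 9.75%
- three tests: 1 - 0.8574 = 14.26%
- five tests (adding capsaicin C2 and C5): 1 - 0.7738 = 22.62%

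Independence is unrealistic for C2 and C5. Both come from the same inhalation series, and by definition C2 cannot exceed C5.

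**2. Correlated tests.** Correlated z statistics were simulated with all nulls true (2,000,000 draws).

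| C2-C5 correlation | Sputum-threshold correlation | C2 or C5 | C2, C5 or sputum ATP |
|---|---|---|---|
| 0.9 | 0.4 | 7.05% | 11.17% |
| 0.8 | 0.2 | 7.81% | 12.28% |
| 0.6 | 0 | 8.77% | 13.30% |

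The C2-or-C5 column does not depend on the sputum correlation.

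**3. What happens when some differences are real.** The last column needs all three nulls to be true.
- Sputum ATP differs and the thresholds do not: a false claim can arise only from C2 or C5, so the chance is 7.0-8.8%.
- The thresholds differ and sputum ATP does not: only one true null remains, so the chance is 5% and there is no inflation.

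The second case is plausible here, because "any signs of cough hypersensitivity would lead to exclusion of healthy controls". It is not certain, since that phrase is undefined and may not cover ATP.

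**4. Whether the three tests form one family.** Sputum ATP is a luminescence assay on stored supernatant. C2 and C5 are responses to an inhaled agent. They answer different halves of the title, and neither document says that success on either would support one joint conclusion. Taken as separate questions, sputum ATP is a single test at 5%. What remains is C2 with C5, at 2.0 to 3.8 percentage points above nominal.

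**5. What a correction would cost.** Holm over the three tests brings the all-null error to 4.0-4.7% over the same correlations. Take a comparison with 80% power at 0.05, so that the mean z is 1.960 + 0.842 = 2.802. At the first Holm step (0.05/3, critical value 2.394), power is Φ(2.802 - 2.394) = Φ(0.408), about 66%. If all three differences are real at that size, simulated Holm power per test is about 73-75%.

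**6. Whether a correction made now would deliver its guarantee.** The 5% bound requires the family, and the test used for each member, to have been fixed before results were known. The SAP leaves the t test, Mann-Whitney and chi-square open, and it is dated about 15 months after January 2024. A Holm family selected at this point would have to be described as post hoc.

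**The case for a change.** The strongest argument for a change does not depend on the simulation. The documents use the language of significance without calling the work exploratory. They measure one of the title's two questions in two unranked ways, and they carry a date after recruitment ended. The remedy is also cheap: either a Holm step on three existing P values or one sentence labelling the analysis exploratory. In addition, counting only three tests understates the load, because capsaicin C2 and C5 and an unlisted number of correlations fall under the same rule.

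The factual part of this stands. Neither document gives a primary endpoint, hierarchy, adjustment or label, and the C2/C5 reading is unstated. A primary outcome may have been recorded elsewhere under the registration number, but that cannot be checked from these documents. The test count is also fair: the three-test figures are not an upper limit on the number of tests made.

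The call for a change does not stand. Holm gives up power for a form of error control that competent statisticians would dispute in an observational patient-versus-control study, which has no treatment claim and no decision rule. The exploratory label, the listing of correlation pairs and the disclosure of dates would help a reader, but none alters a test, an estimate or a P value. Both thresholds are already recorded, so an analyst can report both and describe any disagreement between them as just that. Ranking them now would not restore prespecification.

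**Conclusion.** The omission is real, but it does not warrant a change to the plan. The part that matters is the pair of ATP thresholds. If neither truly differs, the chance that at least one is called significant is about 7.0-8.8% rather than 5%, on an assumed C2-C5 correlation of 0.9 to 0.6. The larger 11.2-13.3% additionally needs sputum ATP to be null and to be pooled with the thresholds, and the title does not require that pooling. Formal adjustment is a trade-off with a clear power cost (80% falling to about 66-75%) and, at this date, no confirmatory guarantee. The lighter options only state what a careful analyst would do anyway: present C2 and C5 together, and read isolated P values just below 0.05 with restraint.

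This conclusion rests on the non-interventional design, on treating the title's two targets as separate questions, and on the assumed correlations.
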